1. PROJECT TITLE

Omega-3 LCPUFA Supplementation in Very Low Birth Weight Infants for The Prevention of Retinopathy of Prematurity: Proposal for a Prospective Randomized Controlled Masked Clinical Trial with Lipidomic and Transcriptomic Analyses

4. ESTIMATED DURATION OF THE STUDY

5 years

5. LAY LANGUAGE SUMMARY OR SYNOPSIS (no more than one paragraph)

Retinopathy of prematurity (ROP) is a blinding disease affecting infants born prematurely. These infants do not have enough essential fatty acids to structurally support the retina, the nerve tissue in the eye which allows us to see. A recent study showed that giving omega-3 (n-3) fatty acids to these infants soon after birth made them less likely to need invasive treatments for eye disease. We intend to give young infants born prematurely with n-3 fish oil treatment and look at how this changes factors in the blood that promote disease. We will do detailed blood studies comparing infants with and without ROP and will follow these infants over time to assess their eye development.

6. SPECIFIC AIMS

The purposes of this study are the following:

- To differentiate the phospholipid profiles and gene expression pathways of at-risk very low birth weight infants with and without treatment with Omegaven® (high n-3 fish oil supplement)
- To establish whether omega-3 fatty acid supplementation in extremely low birth weight infants will reduce the incidence and severity of retinopathy of prematurity (ROP)

7. BACKGROUND AND SIGNIFICANCE

Clinical:

Approximately 517,000 infants are born prematurely every year¹, and as low birth weight and premature infants are surviving longer, they are at high risk of developing severe ROP. In the United States, 2,000 infants per year are diagnosed with severe ROP, which is the leading cause of irreversible childhood blindness in the United States. In our NICU, we care for between 60 and 80 infants each year that are born with low birth weight.

Usual parenteral nutrition protocols do not meet the infants' fetal accretion rates. Despite receiving 14-28 mg DHA/kg/day,² preterm infants have lower serum DHA and EPA levels than they would have had *in utero*, and

their tissues have lower n-3 and n-6 fatty acid than full term infants, indicating that their dietary needs are often not met.³ Preterm and small for gestational age infants have altered serum phospholipid fatty acid profiles with lower DHA and polyunsaturated omega-3 fatty acids than appropriate for gestational age infants.⁴ Low birth weight infants often have severe lung disease and are exposed to exogenous oxygen, which causes retinal blood vessel attenuation, retinal hypoxia, up regulation of pro-angiogenic factors, and neovascularization, which can lead to irreversible vision loss.

In a recent Polish prospective interventional study, Pawlik et al. showed that in preterm infants (average 28 week gestation, 935 gram birth weight), continuous intravenous n-3 fatty acids with Omegaven® from day one to day 28 of life, followed by enteral omega-3 fatty acids is safe and resulted in a significantly decreased need for ROP laser treatment. In the treatment group, 9 of 60 infants needed laser compared with 22 of 70 infants in the control group.^{7,12} On treatment, infants had higher plasma and red blood cell DHA levels at 7 and 14 days and a lower risk for cholestasis. This study showed that treatment was well tolerated in preterm infants and that Omegaven® has a positive effect on ROP pathogenesis, but no investigations were done into the mechanisms by which ROP was suppressed in the experimental group compared with the control arm. There is also no clinical data that currently differentiates the differences in the blood biology (fatty acids, gene expression, and proteins) in infants with and without severe ROP.

Translational:

An oxygen-hypoxia-ischemia mouse model of ROP was developed and used to examine the effects of n-3 PUFA rich (Japanese) and n-6 PUFA rich (western) diets on retinal vascular development in a model of severe ROP. The study showed that there was less retinal vascular obliteration and neovascularization in pups raised on a diet with 2% total fatty acids with n-3s with a 1:1 ratio of DHA: EPA in contrast to a diet in which the 2% total fatty acids were consistent with n-6 fatty acids.⁴ The n-3 diet had a 50% protective effect against pathologic neovascularization due to increased regrowth of vessels after vessel loss,⁶ and this was replicated by giving downstream mediators of n-3 fatty acids (resolvins and neuroprotectin). Inflammatory mediators, including TNF- α , were also lower in the n-3 group, and neovascularization was attenuated via a *PPAR- γ* (independent of VEGF).^{7,2} In mice, EPA supplementation has been shown to increase serum IGF-1, correlating with less risk for ROP. n-3s are a new target for ROP treatment.⁸

Basic:

Docosahexaenoic acid (DHA), a vital dietary long chain polyunsaturated fatty acid (LC-PUFA) is a key component in the sensory and vascular retina. Eicosapentaenoic acid (EPA), a substrate for DHA, is the parent fatty acid that affects eicosanoids implicated in abnormal retinal neovascularization, vascular permeability, and inflammation.⁹ EPA depresses vascular endothelial growth factor (VEGF)-specific tyrosine kinase receptor activation and expression, a key driving force in the pathologic neovascularization.⁹ DHA is antinflammatory, neuroprotective, and also protects against neovascularization.

Safety:

In the recent Polish prospective interventional study, Pawlik et al. showed that in preterm infants (average 28 week gestation, 935 gram birth weight), continuous intravenous n-3 fatty acids with Omegaven® from day one to day 28 of life (n=60), followed by enteral omega-3 fatty acids is safe, and no adverse events or increase mortality or morbidity was noted in the treatment group.^{7,10} At the Children's National Medical Center in Washington DC, Omegaven® was given to ten premature infants with a median gestational age of 26.4 weeks (range, 23.7–34.0 weeks) with hyperbilirubinemia. They showed that the treatment was well tolerated, and there were no adverse events.¹¹ The drug Omegaven is now FDA approved but not for the use specified in our study.

In a recent Cochrane review, LC-PUFA supplementation is considered safe in preterm infants with no increase in morbidity or adverse events.^{2,12,13,14,15,16,17,18}

8. PROGRESS REPORT

Not Applicable; this is a new study

9. RESEARCH DESIGN AND METHODS

The treatment duration for the study will begin 0-7 days of life and continue until 40 weeks adjusted age (full-term). Intravenous treatment will start in the first few days of life and will continue until the infant can tolerate enteral nutrition. Once enteral feeds can be started, supplementation by mouth will begin until 40 weeks adjusted age.

Laboratory blood draws:

Prior to enrollment: In addition to routine tests, blood will be tested for AST and ALT. If these tests are interpreted as abnormal, the infant will not be considered for enrollment in the study as it will be deemed a contraindication to supplemental Omegaven.

While the infant is growing in the hospital, the doctors will need to check the infant's blood to make sure the infant is developing as expected.

If the infant is enrolled in the study, the infant will be randomized in blocks of 4 by gestational age to one of two groups. The control group will get standard of care nutrition, and the experimental group will get standard of care nutrition with supplemental omega-3 fatty acids. Soon after birth, most premature infants need additional nutrition through the vein (intravenous). For the control group, there will be no changes to the standard of care parenteral nutrition. For the experimental group, the infant will receive Omegaven, an intravenous lipid preparation prepared from highly refined fish oil, in addition to the standard of care parenteral nutrition. In the instance that twins are enrolled in the study, the siblings will be randomized as one to receive the same treatment per request and approval from [name].

Transition – For the second/interventional group, Omegaven will be stopped once enteral feeds are at 120 ml/kg and enteral Oil will be started. There will be no overlap of parenteral and enteral n-3 supplementation.

If the infant can start using his/her own stomach for digestion, he/she will get fatty acid supplementation. In the control group, the infant will receive standard of care feeding. If the infant is in the experimental group, the infant will get one fourth (1/4) teaspoon per kilogram per day ($1.25\text{mL/kg/day} = 400\text{ mg omega3 per kg of fish oil per day}$) of Carlson's fish oil oral solution. Dose will be divided to at least twice a day dosing for better tolerance.

Fatty acid supplementation will continue until the baby is full term (40 adjusted weeks of age). If the infant is discharged before he/she is full-term, the infant will be sent home with a bottle of the fatty acid oral solution for the infant to continue daily until he/she is full-term (40 weeks of age). The infant's nutritional needs will be carefully monitored by his/her doctor and nutritionist per NICU protocols.

To monitor the amount of fatty acid nutrition getting into the blood, we will check the infant's blood. As much as possible, we will coordinate the study blood collection at the same time as the routine NICU blood draws. We will collect 1.3 milliliters of blood at 4 different times spread apart while the infant is in the hospital. At each time point, we will collect about 1/4 teaspoon of blood, for a total of about 1 teaspoonful.

The blood draws will occur as the following four time points:

- Blood draw T0= Prior to parenteral nutrition, within 1st 3 days of life. This blood collection should be

taken from cord blood. If cord blood is not available, sample will be collected from a UAC, UVC, or peripheral blood draw concurrent with SOC.

- Blood draw T1= 5 days after parenteral nutrition is started; grace period +/-3 days therefore total 2-8 days after parenteral nutrition started.
- Blood draw T2= 5 days after enteral nutrition full feeds have arrived; grace period +/-3 days therefore total 2-8 days after full enteral nutrition arrived.
- Blood draw T3= Prior to discharge from hospital coinciding with time that ROP may be present, ≥ 35 weeks adjusted age.

This blood will be used for looking at what new genes (mRNA) the infant is making and to check how many and what kind of fatty acids the infant has in the blood. Before testing, the blood will be stored in a storage facility at the UCSD Department of Ophthalmology Blood Bank and labelled with a barcode without the infants' personal information. This is not the infant's DNA, and no DNA will be isolated or tested. Samples will be stored for 10 years. After this time point, all samples will be destroyed if not used by that time. If the parent decides to withdraw consent the blood samples that were already drawn will be destroyed, however, any previously obtained data from sample testing will be kept.

We will examine the infant's eyes according to the standard NICU guidelines and protocols. We will also examine the infant's eyes in our eye clinic after discharge over time as we do for all premature infants to support the infant's visual development.

During the study:

Maternal diet questionnaires will be administered to the maternal subjects following enrollment. This questionnaire is the Omega 3 Fatty Acid Questionnaire and has been validated in a related study for this fatty acid¹⁹. It is anticipated to take 10-15mins to complete. Mothers will be asked to complete this questionnaire at the time of enrollment.

Blood samples will be collected 4 times. When possible, and in the majority of blood draws, 1.3 cc of whole blood will be collected at the same time as other blood draws to avoid multiple sticks. Whole blood will be collected in a green or lavender top tube. One hundred μ l of plasma will be isolated, and this will be aliquoted into in two tubes and frozen (-80°C).

Lipidomics: Plasma fatty acids will be tested using a preprandial whole-blood sample (1.3 mL) drawn 2-4 hours after the parenteral nutrition (PN) had ended for the day and after enteral feedings were held for 3 hours if the patient was also fed enterally. The schedule for sampling will be as follows: prior to parenteral nutrition within ≤ 3 days of life; within 5-8 days after parenteral nutrition is started; within 5-8 days after enteral nutrition full feeds is started; and prior to discharge from hospital coinciding with time that ROP may be present. The samples will be sent to [name] of Engineering in Medicine Laboratory at UCSD or another UCSD laboratory for internal validation of assays. [name] lab (UCSD Department of Ophthalmology) or another laboratory with similar capabilities will perform some of the RNA isolation and analysis. Capillary gas chromatography/mass spectroscopy will be the one of the main methods used to determine the phospholipid profile.

Transcriptomics: From the plasma isolated from the whole blood samples, 50 μ l will be used for mRNA isolation. This will be collected and frozen as the study is ongoing. The fold expression of genes associated with the fatty acid synthesis pathway, hypoxia and pro-angiogenic pathways will be correlated with clinical disease.

Eye exams: All infants will get eye exams according to standard NICU protocols. Serial eye exams will be performed according to the usual intervals, which is until retinal vascularization has matured or active ROP has stabilized, usually at 1-2 months post-term. The area of vascularized retina, clock hours of neovascularization, and amount of retinal vascular dilation and tortuosity will be measured by indirect ophthalmoscopy in all infants at each clinical exam by an ophthalmologist masked to the treatment group. Stage of retinopathy of prematurity and need for ROP treatments will be measured at 40 weeks gestation plus or minus three weeks and followed over time. Infants with ROP will be monitored over time for longer term visual and anatomic outcomes. For both groups, infants will have SOC eye examinations prior to discharge around 40 weeks GA (≥ 38 wks GA). For both groups, if infant is discharged prior to 38 weeks GA, we will collect follow-up data from their outpatient follow-up eye exam from UCSD or other provider

Nutrition: Omegaven has been approved by the FDA for use in children and infants with parenteral nutrition associated liver disease (PNALD). In this study we intend to use Omegaven under an IND exemption to study the use of the drug in reducing the incidence and severity of retinopathy of prematurity (ROP). Our aim is to differentiate the phospholipid profiles and gene expression pathways of at-risk very low birth weight infants with and without treatment with Omegaven® (high n-3 fish oil supplement) and to establish whether omega-3 fatty acid supplementation in extremely low birth weight infants will reduce the incidence and severity of retinopathy of prematurity (ROP). The study intervention “drug product” has been used in the neonatal population via the same route of administration safely for other disease indications internationally and nationally including here at University of California San Diego. This investigation does not significantly increase the risk or decrease the acceptability of risk of our study population.

Infants in the experimental group will be getting Omegaven® for parenteral nutrition in addition to the standard nutritional requirements (Intralipid within a 3:1 TPN). Omegaven dose will be dosed per weight to give goal dose of 1 g/kg/day infused over 12 to 24 hours with the intention to run over 24 hours. Initial Omegaven dose will be between 0.5 g and 1 g/kg/day. If the infant’s nutritional lipid requirements are for more than 1g/kg/day, the remaining calories from fat in the experimental group will be derived from Intralipid (the parenteral lipid emulsion used most often in the UCSD’s NICU). Additional triglyceride testing should not be necessary given dosing²⁰.

Infants in the control group will be getting the standard of care, which is Intralipid® combined with the standard nutritional requirements in a 3:1 TPN. Intralipid will be used according to the Dosage and Administration information in the package insert up to 3.5 g/kilo/day. Initial dose is between 0.5 g and 1 g /kg, starting at 18:00 and running for 24 hours. Total daily dose will be infused over 12 or 24 hours based on provider preference.

Once enteral nutrition reaches desired minimum mL/kg/day (determined by the NICU neonatology team), then parenteral supplementation will be discontinued and enteral supplementation will begin. Carlson’s Fish oil ® (400 mg of omega 3 fatty acids: EPA 200 mg, DHA 125 mg, and 75 mg of other omega-3 fatty acids per ¼ tsp) will be given in the experimental group. Enteral fish oil supplementation of 1.25mL/kg/day (1/4 teaspoon per kg per day) divided at least every 12 hours for tolerance will be continued until the baby is at 40 weeks adjusted age or the retina is fully vascularized. We will adjust our fish oil dosage to maintain maximum enteral DHA supplementation to 125 mg/kg/day (omega3 400mg/kg/day). The total dose will be given BID initially. If there are any symptoms of GERD or other intolerance symptoms that are concerning to the primary team, then oral fish oil total daily dose will be divided over multiple administrations. If enteral oil is not tolerated even after medical management, we can decrease the amount by 25% until tolerated. We do not expect poor tolerance to this dose given 120 mg/kg/day has been tolerated as an emulsion via feeding tube without any complications²¹. As it is typical of this study population to require varying needs of care and drug administration, should any infant randomized to the Omegaven arm require discontinuation of the study drug for clinical reasons for more than

five days (either consecutive or accumulative), that infant will be withdrawn from the study. Drug administration disruptions occurring for 5 or less days (total) shall not be considered protocol deviations but will be recorded and noted in the annual FDA safety report.

Following discharge from the NICU and prior to infants reaching 40 wks, a research team member (other than the PI) will contact the parents with infants in the Omegaven arm once weekly to encourage parents to continue with the prescribe fish oil administration for their infant until he/she has is 40 weeks adjusted age.

The investigational drug pharmacy (IDS) will obtain the Omegaven and dispense it to the nurse for administration in a separate line than the rest of the nutrition (amino acids, sugars, etc). The NICU nutritionist will optimize the total nutritional calories to the infant per NICU protocols. The IDS pharmacist, nutritionist, and NICU team will not be blinded to ensure that the infant in the Omegaven group meets all the nutritional requirements as determined by the NICU neonatology attendings and fellows involved in the study. The ophthalmology team will be blinded to the treatment group to prevent any potential for bias during the eye exam.

Outcome Measures:

Outcome 1: Change in concentrations of basic fatty acids (EPA, DHA, and AA) and their bioactive metabolites will be assessed at multiple time points.

Outcome 2: Change in mRNA expression of TNF- α , PPAR- γ , and VEGF at multiple time points.

Outcome 3: Severity stage of ROP in Group 1 compared to Group 2. This will be assessed at the time of ROP screening (approximately 31 weeks), and the outcome will be measured at approximately 40 weeks adjusted age. The stage of ROP at 40 weeks adjusted will be used for statistical analyses.

Safety:

A data safety monitoring board (DSMB) will be established to monitor the safety of enrolled infants in the study as well as identifying the efficacy of the treatment at ongoing intervals. The DSMB will meet after the first 5 infants are enrolled and then regularly at multiple intervals during the study. Clinical safety assessments will occur during the hospital admission including vital signs, weight, physical exam and laboratory assessments of triglycerides. The neonatologist will review the assessments and determine if the subject should remain in the study or be removed.

Statistical Analysis

Our primary analytic approach will use generalized linear mixed models (GLMM). These methods will address problems of missing data, variable timing of the subject visits, and other possible unintended violations of design. Although our retention and follow-up plan is designed to minimize missing data, an advantage of the GLM models is that they allow us to maximize statistical power by not excluding subjects with some missing data. More specifically, GLM assumes that the data can be missing at random (MAR) or missing completely at random (MCAR). The benefit of this assumption is with a repeated measure problem (e.g., longitudinal data) you can still analyze data from all subjects, even if some have missing data (assumed MAR or MCAR). Mixed regressions will also allow us to estimate an intercept and slope for each patient based on all available data for that individual augmented by the data from the entire sample, with two random effects being used to model time trends (i.e., a random intercept and a linear trend). Further details of selected analyses related to each outcome are provided next.

For Outcome (a-b), the primary outcome is DHA at a specified period of time (i.e. 40 weeks) to assess the basic fatty acids. Outcome (a) posits that patients in Group 1 will differ from those in Group 2 with respect to i) DHA

ii) EPA iii) AA iv) bioactive metabolites. To assess Outcome (a) (i.e. to evaluate the effects of group, time, and their interaction on the change from baseline DHA measurements), a mixed effects model with group (IV Omegaven then PO baby fish oil or Intralipid), time, and group by time interaction as fixed effects, and random intercept and slope to account for within subject correlation. We expect that the interaction in question will be significant.

For Outcome (c), we hypothesize that Group 1 and Group 2 will have a different severity stage of ROP. To assess Outcome (c), we will use a *Mixed-effects ordinal logistic regression model* with severity stage of ROP after 40 weeks (Stage I, II, III, IV, V) as the outcome variable. The same fixed and random effects mentioned above will be used in evaluating Outcome(c).

All statistical analyses will be performed using SAS software version 9.3 (SAS Institute, Cary, North Carolina, USA).

[figure not shown]
Power Calculations

The power calculations that follow were conducted using the software PASS and are based on two-sided tests, with a 0.05 type I error rate. A sample size N=40 was assumed. Power calculation for the primary outcome is presented below.

Power for Outcome (a)

Outcome (a) tests the effect that Group 1 has a different average DHA measurement compared to Group 2. The power calculation for Outcome (a) was based on a two-sided two-sample t-test with a dependent continuous variable (i.e. pre-post difference in DHA measurements) on a categorical independent variable (i.e. Group 1 and Group 2) with a sample size of 40 total subjects. These subjects were equally distributed between each of the two treatment groups. In Pawlik et al. (2013), the mean pre-post difference were 42 $\mu\text{mol/L}$ for patients in Group 1 and 27 $\mu\text{mol/L}$ for patients in Group 2. Following Pawlik et al.'s sampling distribution, we also considered 6 common standard deviation estimates for the power calculation 5, 7, 9, 11, 13, and 15. It should be noted that as the common standard deviation within the group decreases, the group will yield greater power to detect an intervention group effect. As illustrated by the curve in Figure 1, we will have over 80% power to detect a mean difference among the 2 groups of average DHA measurements with a common standard deviation of 15, which is the smallest difference that we can detect with the proposed sample size.

Figure 1: Power for Group Effect on the DHA at 40 weeks.

Note: Even though the data analysis plan relies on longitudinal methods (GLMM), due to unavailability of estimates for repeated measures, the above power calculations were based on a single time point method (two sample t-test). However, the use of a longitudinal method generally results in an increase in power, therefore we believe we will retain sufficient power for the study based on the methods proposed here.

In addition, we have determined that in order to reach a targeted sample size of 40 subjects completing treatment, we will need approximately 60 subjects enrolled to this protocol. This is our target accrual.

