10. HUMAN SUBJECTS

The University of California, San Diego (UCSD) is the only site participating in this study.

We anticipate enrolling 60 infants and up to 60 mothers at UCSD. We will consider patients for enrollment into this study for 5 years.

INFANT:

Inclusion Criteria:

- Infants born \geq 23 weeks gestation and \leq 30 weeks gestation or less than 1500 g at birth.
- Infant whose parent or guardian signed the written consent and HIPAA form.

Exclusion Criteria:

- Patients with liver disease attributable to known causes (i.e. genetic disease, hepatitis) and/or bleeding or clotting abnormalities will be excluded as shown by LFTs.
- Infants $<$ 23 weeks gestation

MOTHER:

- Any mother 18 years of age or older that allows their infant to be enrolled.
- Proficiently English speaking/reading and can complete questionnaire

Infants may still be enrolled in this study if the mother declines to be also participate in the study.

Participation in research is entirely voluntary. Parents of subject may refuse to participate or withdraw at any time without penalty or loss of benefits to which they are entitled. If the parent of subject decides that he/she no longer wishes to continue in this study, the subject's parents will be required to notify the study doctors, [name] or her research staff by calling her at [contact].

The study doctor may decide to take the subject off of the study without the parent's consent if:

- Subject is unable to meet the requirements of the study;
- Subject's medical condition changes;
- New information becomes available that indicates that participation in this study is not in the subject's best interest;
- If the study is stopped,
- The sponsor of the study or the competent authority has the right to withdraw the subject from the study without the parent's permission,
- The study physician can withdraw the subject from the study without the parent's consent if he/she comes to the conclusion that further participation is not in subject's best interest. This can be due to disease or side effects or because subject does not comply with study procedures

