11. RECRUITMENT

Waiver of Consent for Aiding in Research Recruitment:

I am asking for a waiver of consent while recruiting subjects because:

It would be minimal risk to the potential subjects while reviewing their private information. For this study, the subjects will already be hospitalized. The PI or sub PI will need to review the subjects' medical records for their routine care and to determine treatment for the subjects. While reviewing the medical records for their standard of care (SOC) treatment, the PI or sub PI may determine that the subject may qualify for the study and then proceed to ask the subject if they would be interested. The PI or sub PI will not review a patient's medical record solely to determine if they qualify for this study.

Reviewing patients' medical records would not adversely affect the rights and welfare of the potential subjects because the patients have already signed a HIPPA form when they were admitted to the hospital. Because the patient signed the form, we are allowed to review their medical records.

We would not be able to determine if the patient qualifies for this study without reviewing their medical records.

We will provide any new pertinent information to the subjects by providing the subject an addendum consent form with the information about this study. The patient will have time review and ask questions before signing the addendum and will be able to withdraw their consent if they desire.

I am asking for a waiver of HIPAA Authorization while recruiting subjects because:

The research staff will only print out medical records from patients when they have signed the consent form and the HIPAA consent form. If we do print out medical records, we will immediately black out any PHI on the documents, then copy the documents, and then again black out any PHI. The charts will be kept in a locked office in a locked cabinet and only the research staff assigned to the study will have access to the charts.

We would not be able to determine if the patient qualifies for this study without reviewing their medical records including their PHI (for example we will need contact information and mailing information).

The benefit of allowing access to the patient's PHI, will allow us to determine if they qualify for this study (for example their birth weight or gestational age).

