26. IMPACT ON STAFF

This study will utilize the neonatology research team to perform all duties in the protocol including performing the procedures/tests for each visit, utilizing EPIC system for reports pertinent to study i.e. lab reports, help with screening, and scheduling appointments. Nursing staff will be responsible for hanging Omegaven infusion with standard of care TPN or hyperal per physician orders.

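### The single stated block size of 4, in a one-site trial with an unmasked NICU team, would let recruiting staff who track earlier allocations know up to a third of assignments before approaching a family

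*Combined protocol and SAP*

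**What the plan says.** All references are to the combined protocol and SAP.

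- **Allocation rule (Section 9).** "the infant will be randomized in blocks of 4 by gestational age to one of two groups". Four is the only size given. The gestational-age strata are not defined. The text does not say who generates or holds the list, or how assignments are concealed. Twins are randomised together, but it is not stated whether a pair uses one slot or two.
- **Ratio (Section 9, power calculation).** The randomisation text gives no ratio. The power section implies 1:1: "These subjects were equally distributed between each of the two treatment groups".
- **Site (Section 10).** "The University of California, San Diego (UCSD) is the only site participating in this study".
- **Masking (Section 9).** "The IDS pharmacist, nutritionist, and NICU team will not be blinded". The investigational pharmacy is to obtain Omegaven and "dispense it to the nurse for administration in a separate line than the rest of the nutrition". No placebo infusion is described for controls. Masking is confined to the eye team: "The ophthalmology team will be blinded to the treatment group to prevent any potential for bias during the eye exam".
- **Who recruits.** Section 11 says that, during routine record review, "the PI or sub PI may determine that the subject may qualify for the study" and may then approach the family. Section 26 says "This study will utilize the neonatology research team to perform all duties in the protocol", and lists help with screening among those duties.
- **Order of events (Section 9).** AST and ALT are read before enrolment, and the text gives no numeric limit for an abnormal result.

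**The concern.** With one known block size, anyone who can count the arms already used in a stratum can work out the last assignment of every block and sometimes the last two. Here the counting is easy: one unit holds every stratum's history, the arm is visible at the bedside, and some of the staff who screen belong to the unmasked service.

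The risk is that whom to approach, or how a borderline screening result is read, comes to depend on the arm that is next. Section 7 reports 60 to 80 low-birth-weight infants a year, and Section 10 plans 60 enrolments over 5 years. That is 300 to 400 infants for 60 places. Not all will be eligible or consent, but there is room for choice.

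ROP stage at about 40 weeks is the outcome most exposed, since it plausibly depends on baseline risk. The mixed models in Section 9 carry group, time and their interaction as fixed effects, with no baseline-risk covariate to absorb an imbalance. Masked eye examinations protect the assessment of ROP, not the make-up of the arms.

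**Working it through.** **The plan's own figure.** The documents give no figure for predictability of allocation. The nearest quantitative statement is power above 80% for change in DHA. With 20 per arm, a difference of 42 − 27 = 15, SD 15 and two-sided 5% error, the noncentral t with 38 df gives 86.9%. The statement is reproduced, and it does not depend on the block rule.

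**Inputs.** Block size 4 (Section 9); 1:1 ratio (implied by the power section); 60 enrolled (Sections 9 and 10). Assumptions: every block uses size 4, and the observer knows the block size, the strata and all earlier allocations in the stratum.

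**Certain allocations in complete blocks.** There are six equally likely blocks. In AABB and BBAA the last two slots are certain. In ABAB, ABBA, BAAB and BABA only the last is.

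(2 × 2 + 4 × 1) / 6 = 1.333 per block; 1.333 / 4 = 33.3%; 60 × 0.333 = 20.

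**Best guess by position.**

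| Slot | Chance next arm is certain | Chance best guess is right |
|---|---|---|
| 1 | 0 | 0.5 |
| 2 | 0 | 2/3 |
| 3 | 1/3 | 1/3 × 1 + 2/3 × 0.5 = 2/3 |
| 4 | 1 | 1 |
| Mean | 33.3% | 70.8% |

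Simple randomisation would give 50% correct guesses.

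**Allowing for strata.** Unfinished blocks lower the share. For m units in a stratum, the expected number certain is 4/3 for each complete block, plus 1/3 if three units are left over. The 60 units were split at random over equal strata (10,000 simulations):

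| Strata | Certain | Of 60 units |
|---|---|---|
| 1 | 33.3% | 20.0 |
| 2 | 31.9% | 19.2 |
| 3 | 31.2% | 18.7 |
| 4 | 30.6% | 18.3 |
| 8 | 27.8% | 16.7 |

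These are counts of randomised units. If a twin pair takes one slot, 60 infants make fewer than 60 units.

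**Other block schemes.** The mixed schemes were simulated (3,000 lists, one stratum, 60 units, sizes equally likely) against an observer who knows the possible sizes and all past allocations. The fixed schemes are exact.

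| Scheme | Certain | Best guess right |
|---|---|---|
| Fixed 4 | 33.3% | 70.8% |
| Fixed 6 | 25.0% | 68.3% |
| Random 4, 6 | 5.6% | 69.0% |
| Random 2, 4, 6 | 4.1% | 70.0% |

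For sizes 2, 4 and 6, 60 × 0.041 is about 2.4 units. Varying the size removes most of the certainty and almost none of the guessability.

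**The case against.** **The recruiter may not know past allocations.** No passage says that the person approaching a family is one of the unmasked staff. Section 9 has the weekly calls to Omegaven-arm parents made by someone who is not the PI, which suggests the PI may be kept from allocation. This stands for the PI. It does not cover the sub PIs or the neonatology team, and Section 26 gives that team a part in screening.

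**A third is not known from the start.** A reader might infer that one allocation in three is fixed knowledge before the trial opens. The documents do not support that. Certainty arises only as each block fills, and only for someone holding all the information assumed above. That the size is fixed is itself inferred from the one size stated.

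**Silence is not absence.** A reader might infer that the list is unconcealed. The documents do not say so, and a procedure, including pharmacy custody, may exist elsewhere. Concealing the list, however, does not stop staff counting visible allocations through a published block size.

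**The powered outcome is little exposed.** Change in DHA is a laboratory measure with a baseline sample, so prognostic selection is a weaker threat there. This stands. The timing route is also narrow: the baseline sample is due within 3 days and treatment starts by day 7, so an infant cannot be held long for a later slot. Choosing whom to approach remains possible.

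**The remedy leaves guessing intact.** This also stands. The 70% rate already assumes a hidden list, so concealment cannot lower it.

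**Conclusion.** The point holds as an avoidable opportunity for selection bias. Up to 33% of allocations would be certain to recruiting staff who know the block size, the strata and the earlier allocations. With two to four equal strata this is about 31–32%, or 18–19 of 60 randomised units. The figures assume a constant block size and a 1:1 ratio; undefined strata and the handling of twins make the exact count uncertain.

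A reader might go further and infer that enrolment will be, or has been, biased. The documents show only that the conditions for it are present, and no effect on either outcome has been quantified. The concern attaches to the sub PIs and the neonatology team, and to ROP stage more than to change in DHA. Because bias of this kind cannot be reliably repaired at analysis and the change is cheap, it should be made.

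**What to change.** Keep the gestational-age strata and define them. Generate the list with randomly varying block sizes, for example 2, 4 and 6. Keep the sizes out of the protocol and from anyone who screens, approaches or enrols families. State who holds the list, and release each assignment only after consent and eligibility, including the reading of AST and ALT, have been recorded. State also whether a twin pair takes one slot or two.

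Varying the sizes cuts certain allocations from about a third to about 4%. Releasing assignments late limits the scope for acting on a guess when eligibility is judged. Neither lowers the best-guess rate, which stays near 70% while past allocations are visible at the bedside, so the protocol should not claim that foreknowledge is eliminated.

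The cost is a new list and a short protocol change. The largest imbalance within a stratum rises from 2 (half of 4) to 3 (half of 6). The power calculation is unaffected.
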